Study staff will have direct contact with participants on 10 occasions during the 8-week study period to assess for any adverse events, medication side effects, and answer questions about treatment. This includes three Study Visits (Day 1, 29, 57), four Medical Monitoring Visits (Day 6, 10, 14, 18) and four Safety Check-ins via phone or electronic survey (Day 2, 36, 43, 50). All study visits will be conducted in the University of Wisconsin-Madison Hospital CRU under medical supervision. A registered nurse will be present in the CRU during all study visits to monitor for drug side effects and provide appropriate medical attention. Orthostatic vital signs will be checked by CRU-RN at all study visits. Any participants experiencing significant side effects will be withdrawn from the study and provided medical attention from the study nursing staff and/or physician as needed. Adverse events will be monitored, and "stopping rules" will be applied if needed (see Stopping rules).

Participants will be educated about potential side effects of doxazosin and ways to mitigate risk. For instance, to reduce the risk of syncope upon standing from bed in the morning, participants will be instructed to slowly sit up and stay on the edge of their bed for 5 minutes before standing following the initial doses of doxazosin. Additional instructions will encourage participants to keep well-hydrated and urinate while sitting down rather than standing. They will be strongly discouraged from driving or operating heavy machinery within 24 hours of the first dose, or at any dose escalation.

It will be recommended that participants continue to take doxazosin before bed, however clinical research has shown that doxazosin is safe to take in morning or evening and with or without food. Doxazosin is not sedating nor are there concerns of rebound hypertension following rapid cessation of use that occur with other noradrenergic agents, such as clonidine¹³¹.

If symptoms of hypotension (such as dizziness) are reported, the participant will be encouraged to increase fluid intake if a negative fluid balance may be playing a role. If hypotension is noted in the CRU settings, the medical staff, upon the study physician orders, is able to place a peripheral venous access and administer IV fluids, such as normal saline, that can provide an effective treatment for orthostatic hypotension.

Participants will be encouraged to continue whatever treatment for alcohol use they were receiving prior to study enrollment throughout the duration of the study. They will be instructed that the study medication is not approved as pharmacotherapy for their alcohol use disorder and therefore will not substitute for their existing treatments and other supports. Participants will be instructed to contact the study staff immediately if they experience any adverse events during these 8 weeks. The study physician will make medical recommendations as appropriate to handle the adverse events. The UW Pharmaceutical Research Center will break the drug blind to inform the participant and study physician if a situation arises where this information is critical to providing appropriate medical care.

Doxazosin in usual medical practice is used to treat high blood pressure and urinary retention associated with benign prostatic hyperplasia; these indications have been associated with certain practices for medication initiation and titration that are optimized for these conditions. In this study, doxazosin is used as an alcohol relapse prevention pharmacotherapy. In this context, the considerations for optimal dosing take into account the risk-benefit ration of a given dose and its titration protocol versus, potential benefits of doxazosin therapy. Research documents the overall safety and superior results of the titration protocols similar to the proposed one, when compared with a slower-titration protocol or placebo for relapse prevention (or improving outcomes) among individuals with substance use disorders (108,148, https://clinicaltrials.gov/ct2/show/NCT01730846). In addition, the risk of alcohol relapse is highest in the first 3 months after stopping drinking in alcohol dependent adults, suggesting that effective interventions, when implemented early in the recovery, have the best potential to prevent relapse. Therefore, both evidence and conceptual framework derived from a natural history of alcohol dependence suggest an increased benefit of the proposed, previously-tested titration schedule in alcohol dependent adults, compared to a slower titration, typical in hypertension or BPH. Although the potential benefit of the proposed titration schedule and dosing appears to outweigh the potential risks (side effects) in this clinical population, we propose additional safeguards (i.e., the dose titration protocol will be modified slower titration, lower final dose) if the participant experiences side effects requiring such a modification.

Serious but rare side effects: We will counsel the participants about the symptoms of priapism, a rare but serious side effect of doxazosin. We will inform them that this condition, if occurs, requires emergent evaluation and treatment. Should these symptoms occur, the study physician and/or the participant's personal clinician will be immediately contacted, and the participant will be directed to go to the emergency department right away. Our clinical experience corroborates the package insert information that this is indeed a rare condition. However, to further mitigate the risk, we have added an exclusionary criterion that those receiving medications commonly prescribed for erectile dysfunction, such as sidenafil or tadalafil, will not be eligible. Recent or current use of trazodone, another medication which can increase the risk of priapism in combination with doxazonsin, is also an exclusionary criteria.

6. Risk of Confidentiality failure: All data will be coded by participant number only and any personal identifiers linking participants to their reports on surveys and questionnaires will be detached and destroyed as soon as participation is completed or disqualification occurs. All data are stored electronically on a secure server in the Department of Psychology, or in two UW sponsored electronic databases Qualtrics (self-report questionnaires, study forms) and OnCore (participant-tracking), which have accepted measures to protect participant confidentiality and are compliant with all national clinical research policies. PHI will link to individuals' participation in OnCore and HealthLink only and only the minimal necessary information will be entered into the participant's medical record in order to protect their confidentiality regarding alcohol and drug use status. In addition, a Certificate of Confidentiality (CoC) has been secured from the National Institute of Alcohol Abuse and Alcoholism in order to protect identifiable research information from forced disclosure. A CoC allows an investigator and others who have access to research records to refuse to disclose identifying information on research participants in any civil, criminal, administrative, legislative, or other proceeding, whether at the federal, state, or local level.

7. Risk of alcohol craving: There is a possibility that following the NPU stressor task in study visits 1 and 2, alcohol-dependent participants will experience alcohol craving, due to the mild stressor exposure. Generally, cravings subside with the simple passage of time. However, all participants will also receive brief (30 minute), standardized Motivational Enhancement Therapy (MET) to support continued abstinence at study visits 1 and 2 following completion of the NPU task. Participants will complete a brief alcohol craving questionnaire, a 6-item subset of the 14-item version of the Desires for Alcohol Questionnaire (DAQ6) upon arrival at the laboratory and after completing all study procedures at each study visit. The items include: "I want a drink so much I can almost taste it", "My desire to drink now seems overwhelming", "I would do almost anything to have a drink now", "I am going to drink as soon as I possibly can", "I would consider having a drink now", "I would accept a drink now if it was offered to me." Participants will be required to remain at the CRU until their craving ratings return to baseline on each item of the scale. In our recent study with 58 abstinent alcoholics, only 5 participants were required to stay in the lab for a brief period of time until their cravings returned to baseline simply by the passage of time.

Thirty minutes of motivational therapy will be administered to participants two times during the regular course of the study. Additionally, if participants report strong cravings or alcohol use, an additional 30 minute session of motivational counseling will be provided to help them to recover their abstinence goals. Referrals to local treatment providers will always be available to participants, and referral to these providers or back to the participant's own treatment provider will be made in case further intervention is warranted.

D3. Potential Benefits of the Proposed Research to Human Subjects and Others

Considering the safeguards outlined above, any potential risks associated with participation in this project appear to have been minimized. There is strong reason to believe that participants assigned to receive doxazosin treatment may have a reduced risk of relapse to alcohol use during the 8 week treatment period. However this is unknown to date and is indeed a goal of the study to determine the efficacy of doxazosin. It is possible that simple accountability related to study participation and contact with research/medical study staff will reduce participants' relapse risk. Including brief MET at study visits 1-2 is likely to further support those goals of relapse prevention.

All participants will be paid for their time invested during study procedures. Participants will be paid \$320 for time spent in visits, plus a \$100 bonus for completing all eight visits, as well as up to \$75 in bonuses for attending/not rescheduling/being on time to all visits, and a \$25 bonus for meeting a 90% threshold for medication compliance. These modest inducements represent reasonable compensation for time spent in the study and are not considered coercive.

Aside from these factors, there is not likely to be any immediate, direct benefit to the participant other than a better understanding of the processes and purposes of psychological and biomedical research acquired through experience and debriefing. However, the knowledge that can reasonably be expected to result from the proposed study has potentially important implications for the field of addiction treatment.

D4. Importance of the Knowledge to be Gained

As indicated above, the risks associated with this research appear to have been minimized. In contrast, the potential importance of the knowledge to be gained and its clinical application is high. Specifically, the costs to both individuals and the society as a whole resulting from alcoholism are high. The research proposed in this application is designed to address potentially important affective and pharmacological mechanisms in the etiology and maintenance/relapse of alcohol dependence. Most importantly, this study aims to investigate the utility of doxazosin as a potential treatment of stress-induced relapse in alcoholism, which is not well treated by any currently available pharmacotherapy for drug addiction.

D5. Data and Safety Monitoring Plan

Monitoring the progress of study and the safety of participants. The Principal Investigator will be responsible for routine monitoring of the study's progress. This includes scheduled monthly meetings with

study staff and the study MD, and review of written documentation. Data that are reviewed at these meetings include the number and type of participants enrolled, the number and reasons for exclusions from enrollment, the number treated and the stage of treatment, summary of adverse events, individual review of serious adverse events and study participation and outcome data. In addition, any unanticipated health events that raise concerns (e.g., serious mood or behavioral changes, suicidal ideation, abnormal test results) will be immediately reported to the PI and the study physicians.

To facilitate participant safety, study participants must meet study eligibility criteria. Once enrolled, study protocol will assess for the presence of adverse events at each study visit by querying participants as to whether they have experienced any adverse side effects associated with study medications. Participants who report development of severe side effects associated with doxazosin (which is unlikely) will be discontinued from further study participation as a precaution. Such events will be immediately reported to the PI and study physicians. If significant psychiatric or medical symptoms are reported, the participant will be referred, as needed, to the appropriate emergency medical or psychiatric services.

Stopping rules. Study will be stopped if two patients experience SAEs diagnosed to be related to the study drug and affect same organ system (e.g., cardiac, hepatic, renal or central nervous system). More specific examples are a three-fold elevation above baseline of serum liver enzyme (hepatic function) and creatinine (kidney function) levels, and QTc interval prolongation over 500 ms (or 50 ms increase over baseline) or other documented serious ECG abnormalities.

The study would resume after thorough evaluation and if it is deemed that the continuation of study activities is determined safe to participants by the study physicians, the study investigators, the IRB, and the funding agency representative.

Plans for assuring compliance with requirements regarding the reporting of adverse events. This Data Safety and Monitoring Plan requires that investigators notify NIH and the University of Wisconsin IRB of the occurrence of any serious adverse event (SAE), or any adverse event (AE), which is severe, unexpected, and possibly related to study medication or protocol. Such notification must occur within five days of investigators becoming aware of the event. If the serious adverse event might be related to drug use, both the Food and Drug Administration and the manufacturer will also be notified within five days of investigators becoming aware of the event. Examples of serious adverse events would be untoward medical or treatment occurrences that result in death, are life-threatening, require hospitalization or prolonging of existing hospitalization, create persistent or significant disability/incapacity, or involve congenital abnormality/birth defects. Unanticipated adverse events would include less serious problems that merit reporting because they are severe, unexpected, and possibly related to study participation. Any serious adverse event (SAE) will be queried and reported even if it appears that the serious adverse event is unrelated to treatment participation. The PI will be responsible for the accurate documentation, investigation and follow-up of all study-related adverse events.

Adverse event assessment, recording, reporting and investigation will be accomplished through staff training, structured or standardized assessments of untoward occurrences/events, and regular monitoring by study investigators. The Principal Investigator has ultimate responsibility for ensuring that serious adverse events are detected and reported in a timely manner. All serious or unanticipated adverse events will be reviewed by the study physicians. Additionally, the IRB will receive an annual report of all serious adverse events and adverse events meeting the criteria listed above.

Plans for assuring that any action resulting in a temporary or permanent suspension of an NIH-funded clinical trial is reported to the NIH grant program director responsible for the grant. The NIH grant program director will be notified within five days if the Principal Investigator deems it necessary to suspend the study. In the case of a temporary suspension, the Principal Investigator will develop a plan for continuation of the study and discuss this plan with the NIH grant program director in a reasonable time frame.

Plans for assuring data accuracy and confidentiality and protocol compliance. The Principal Investigator will refine existing protocols for assuring data accuracy and protocol compliance. Such protocols will include

data verification and protocol compliance checks as well as other quality assurance procedures. The Principal Investigator will also be responsible for ensuring that the data for the project are securely stored, that storage is in compliance with University and federal regulations and that no unauthorized persons have access (electronic or physical) to any participant-identifiable data.

Data and Record Keeping:

Data Management

Study staff will collect and maintain all information on secure servers managed by the university, including the university Qualtrics and OnCore servers, or on a private secure server managed by the research team. Any hard copy study data will be kept in a locked cabinet which only the Project Director and Project Coordinator can access, in a locked room in the Psychology department in [name] laboratory.

The Principal Investigator will oversee data verification and protocol compliance checks as well as other quality assurance procedures. The Principal Investigator will also be responsible for ensuring that the data for the project are securely stored, that storage is in compliance with University and federal regulations and that no unauthorized persons have access (electronic or physical) to any participant-identifiable data.

Confidentiality

The UW Institute of Clinical and Translational Research (ICTR) provides UW researchers with comprehensive data management software tools (Online Collaborative Research Environment; OnCore) and support, which helps ensure confidentiality of data. The self-report and psychophysiological measures that will be used in the proposed research are generally of a benign nature. However, some self-report questionnaires could yield sensitive information. Consequently, all data will be coded by participant number only and any personal identifiers linking participants to their reports on surveys and questionnaires will be detached and destroyed as soon as participation is completed or disqualification occurs.

Data Collection Methods

All research materials obtained from participants will be collected directly from them. They will consist exclusively of self-reports, medical evaluations, biological samples, and records of psychophysiological responding. There will be no use of archival records or other such data.

Surveys and interviews will be administered to the participant by study staff via iPad. The iPads access the University's secure Qualtrics account and data is entered there directly. At no time is data ever saved on the iPads.

Physiological data is collected by study staff using our lab's psychophysiology equipment, and saved directly to our secure server in the Department of Psychology

Biologic samples (blood, urine) will be collected by medical staff at the Clinical Research Unit (CRU) according to standard medical practice, and handled and disposed of using standard CRU procedures.

Smart cap data will be stored in an online password protected platform. All data stored on this platform is coded only.

The SCID-RV interviews and the MET sessions will be audio recorded. The SCID or MET clinician will review these recordings alongside the licensed clinical psychologist for supervision purposes. These recordings will be deleted immediately after review.

Study Records Retention Policy

All de-identified data and associated study documents will be archived according to IRB and University policies and retained for seven years.

In accordance with Federal Open Access policies, de-identified datasets and analysis materials will be made available using approved Data Sharing practices identified by the University's Research Data Services.

Bibliography and References

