| SAFETY & COMPLIANCE | | | | | | |
| Study visit monitoring | Vital signs; Adverse events | | Х | | Х | Х |
| Treatment monitoring | Monitoring visits: Adverse events; vitals | | | Х | | |
| Treatment monitoring | Staff phone calls: Adverse events | | | | Day 2, 36, 43, 50 | |
| | Phone call reminder | | | Х | Х | Х |
| Medication compliance | Pill counts; self-report | | | X | Х | Х |
| | Review of smart caps logs (opening times/dates) | | | X | Х | X |
| Behavioral intervention | Brief motivational intervention (following NPU task) | | Х | | Х | On lapse |
| Acute craving (for study release) | Desire for Alcohol Scale (following NPU task; repeat as needed) | | Х | | Х | |
| OUTCOMES | | | | | | |
| Stress reactivity | Startle potentiation and self-report negative affect in NPU task | | Х | | Х | |
| | Perceived Stress Scale | | Past w eek | Past w eek | Past w eek | Past w eek |
| Alcohol use | Blood alcohol concentration (via breath test) | Х | Х | X | Х | Х |
| | TLFB (continuous abstinence, days drinking/w eek, drinks/day) | | Since last visit | Since last visit | Since last visit | Since last visit |
| Craving | Penn Alcohol Craving Scale | | Past w eek | Past w eek | Past w eek | Past w eek |

C4. Doxazosin Dosing Schedule

| TABLE 2 | TREATMENT DAY | DISPENSATION DAY (mg/capsule) | DAILY DOSE |
|-----------|---------------|-----------------------------------|------------|
| TREATMENT | 1 - 5 | Day 1: Study Visit 1 (1 mg) | 1 mg qd |
| | 6 - 9 | Day 6: Monitoring Visit 1 (2 mg) | 2 mg qd |
| | 10 - 13 | | 4 mg qd |
| | 14 - 17 | | 6 mg qd |
| | 18 - 28 | Day 18: Monitoring Visit 4 (4 mg) | 8 mg qd |
| | 29 - 56 | Day 29: Study Visit 2 (4 mg) | 8 mg qd |
| TAPER | 57 | Day 57: Study Visit 3 (6 x 1 mg) | 6 mg qd |
| | 58 | Day 58 (4 x 1 mg) | 4 mg qd |
| | 59 | Day 59 (2 x 1 mg) | 2 mg qd |
| | 60 | Day 60 (1 x 1 mg) | 1 mg qd |

All doxazosin and matched-placebo capsules will be prepared and blinded by the University of Iowa Pharmaceuticals, randomized by the UW Pharmaceutical Research Center and distributed through the UW CRU. Half the participants (N=80) will receive doxazosin and half (N=80) will receive a matched number of placebo pills daily for 8 weeks of

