treatment. The target therapeutic dose (8 mg doxazosin) will be achieved after an 18-day dose escalation schedule. Medication will be distributed across 6 visits. Participants will be provided 3-5 days of extra pills of their current dose at each distribution to provide flexibility in missed appointments; however, participants will not receive their next escalated dose until they attend an in-person visit. On study completion all participants will taper off doxazosin (or placebo) over 5 days using a protocol successfully employed by our consultant [name] in a recently completed smoking cessation trial. Participants who withdraw from the study will be tapered using the same protocol. There are no adverse effects with rapid cessation that may occur in other noradrenergic drugs (e.g., propranolol rebound hypertension)¹³¹.

C5. Medical Monitoring And Medication Compliance

[figure not shown]
Participants' safety will be evaluated by the study staff and medical staff via measurement of vital signs and self-report of medication side effects, adverse events, medication compliance and alcohol use at each of the three Study Visits (Day 1, 29, 57). Study staff will call participants on Day 2 to monitor (via self-report) adverse events and initial compliance with taking the first pill on Day 1. In addition, participants will attend four additional Medical Monitoring Visits at the UW Hospital the day of each dose escalation (Day 6, 10, 14, 18) for similar evaluation. As such, participants are evaluated in person prior to each dose escalation and at 4 weeks and 8 weeks into treatment.

Participants will complete safety check-ins weekly between Study Visit 2 and 3 (Day 36, 43, 50) to evaluate safety via self-report of medication side effects, adverse events, medication compliance, and alcohol use. These check-ins can occur via phone call or electronic survey according to participant preference. For participants who opt for electronic surveys, study staff will follow-up via phone if the participant reports side effects or problems or if the participant does not complete the survey. While we anticipate that subjects will tolerate study medication well, should participants experience adverse medication side effects, titration will be stopped at the highest tolerable dose. Maximum achieved dose will be included as a covariate in preliminary statistical models.

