On arrival at the Clinical Research Unit (CRU) in the University of Wisconsin Madison Hospital for the first study visit all participants will complete medical screening that will include review of medical history, review of medications, and screening clinical exam conducted by the provider. Medical staff will conduct clinical assessment to determine vital signs (including sitting and standing blood pressure and heart rate determinations). Twelve-lead ECG will be obtained in all participants. Laboratory evaluation will include chemistry panel comprehensive metabolic profile (Chem-12, assessing kidney and liver function, glucose level and electrolyte status), complete blood count (CBC), and thyroid stimulating hormone (TSH). All study visits will include blood alcohol concentration (BAC) breath-testing. A pregnancy test for women of childbearing potential will occur at all visits with the exception of Visit 3. This is not needed at Visit 3 as tapering the dose, which would be the response to a positive pregnancy test, will happen at this visit for all subjects.

Clinical assessment, clinical exam, and all other medical and medication screenings and monitoring will be conducted by medical staff. ECG interpretations will be confirmed by the study physician. All measures are reviewed by study staff to ensure that participants can safely use doxazosin and participate in the study. Specifically, participants will be excluded for FDA contraindications for doxazosin. All women of childbearing potential will be required to agree to use a study-approved method of birth control or abstinence to prevent pregnancy during the course of the study. Medically-related issues, if needed, will be discussed by the research staff and medical staff with a designated study physician who will be timely available via pager or cell phone.

Exclusion criteria are divided into three broad categories of Medical, Psychiatric/Behavioral, and Medications/Therapies. These criteria are all implemented to protect human subject safety, except where noted with an asterisk (*) denoting scientific/theoretical reasons. See Appendix C (Eligibility Criteria Checklist) for detailed description of eligibility criteria, assessment measures and assessors.

Medical exclusion

- Past or current coronary artery disease, cerebrovascular accident, unstable angina, history of myocardial infarction, history of congestive heart failure.

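### Study drug is taken on a taper after Visit 3, but the last scheduled adverse-event query is at Visit 3 on Day 57; a minor safety gap that one check-in would close

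*Combined protocol and SAP*

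**What the plan says.** Dosing continues past the last visit. Section C4 says "On study completion all participants will taper off doxazosin (or placebo", and the last row of Table 2 reads "Day 60 (1 x 1 mg) | 1 mg qd". Section D1 explains why no pregnancy test is needed at Visit 3: "tapering the dose, which would be the response to a positive pregnancy test, will happen at this visit for all subjects". Section C4 adds: "Participants who withdraw from the study will be tapered using the same protocol". The text of C4 gives the taper as five days, while Table 2 lists four dosing days (57 to 60).

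Safety contacts stop at Visit 3. D2, item 5 lists three study visits (Days 1, 29, 57), four monitoring visits (Days 6, 10, 14, 18) and "four Safety Check-ins via phone or electronic survey (Day 2, 36, 43, 50". Table 1 and C5 give the same days. The general commitment in D5 is that "study protocol will assess for the presence of adverse events at each study visit", and no study visit follows Day 57. The only later contact mentioned (C3) is an unblinding call for some participants who consented under an earlier protocol, and it is not a safety query.

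Two other provisions bear on the taper. The daily text prompts in C5 ask participants to contact staff about side effects; no end day is given. D2, item 5 tells participants to report adverse events at once, but the instruction is worded for the eight-week period.

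**The concern.** During treatment, every stretch of dosing is followed by a scheduled occasion on which someone asks about adverse events. The taper is the exception. A site that follows the plan exactly hands over the reduced doses at Visit 3, debriefs and pays the participant, and does not ask again. Events on the last doses then enter the safety record only if the participant calls in.

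What is at stake is the completeness of adverse-event ascertainment while participants are still on study drug. D5 says that serious adverse events will be queried, and its stopping rule counts drug-related serious events. Neither has a scheduled occasion to pick up an event during the taper.

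Early withdrawals deserve particular notice. D2 says that any "participants experiencing significant side effects will be withdrawn from the study and provided medical attention from the study nursing staff and/or physician as needed", and C4 gives withdrawn participants the same taper. Someone who has just tolerated the drug badly may therefore take further, falling doses with no stated follow-up query.

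**Working it through.** The plan gives no figure of its own to reproduce here. The check sets the dosing days against the query days.

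**Inputs**
- Taper doses (Table 2): 6, 4, 2 and 1 mg on Days 57, 58, 59 and 60. The C4 text gives five days.
- Scheduled adverse-event queries (Table 1, C5, D2): Days 1, 2, 6, 10, 14, 18, 29, 36, 43, 50, 57. These are 3 + 4 + 4 = 11 contacts. D2 states 10, but the latest day is 57 on either count.
- Arm size (C4): 80 per arm, 160 in total.
- Completion (Timeline): 85%, assumed equal in the two arms.
- Timing of the dose (D2, item 5): "It will be recommended that participants continue to take doxazosin before bed". Morning dosing is described there as safe too. The 6 mg taper dose is dispensed at Visit 3.

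**Step 1: intervals between queries.** Successive gaps are 1, 4, 4, 4, 4, 11, 7, 7, 7 and 7 days. The longest, 11 days (Day 18 to Day 29), is longer than the taper, but a visit then asks about it. No query follows Day 57.

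**Step 2: dosing days with no later query**

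| Reading | Days | Share of dosing days |
|---|---|---|
| Day 57 dose precedes the Visit 3 query | 3 (Days 58-60) | 3/60 = 5.0% |
| Day 57 dose at bedtime, Table 2 taper | 4 (Days 57-60) | 4/60 = 6.7% |
| Day 57 dose at bedtime, five-day taper (C4 text) | 5 (Days 57-61) | 5/61 = 8.2% |

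**Step 3: scale.** Expected doxazosin completers: 80 x 0.85 = 68. Doxazosin dosing days with no later query: 68 x 3 = 204, 68 x 4 = 272, 68 x 5 = 340. This assumes that every completer follows the full taper. C5 allows titration to stop at a lower tolerated dose, so the true totals could be somewhat smaller. The documents do not give the number of early-withdrawal tapers.

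**Step 4: when a check-in would be informative.** A6 gives a half-life of 16 to 22 hours. Assume one compartment, immediate absorption and the Table 2 taper. With k = 0.5^(24/half-life), the steady-state peak on 8 mg is 8/(1 - k), and each taper day updates the amount as (previous amount x k) + dose. Relative to that peak, the amount remaining after the Day 60 dose is:
- at 24 hours: 8% (16 h half-life) to 13% (22 h)
- at 48 hours: 3% to 6%

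A contact within a few days of the last dose therefore looks back over essentially the whole exposure.

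**The case against.** The strongest reply is that nothing in the documents marks the taper as hazardous. The doses fall, and a participant on the full schedule has already taken these dose levels during escalation, with an in-person evaluation before each increase. C4 anticipates no adverse effects of rapid cessation of the kind seen with other noradrenergic drugs, and D2 dismisses rebound hypertension. All of this stands, and it sets the weight of the point.

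It can also be said that the existing cover is wider than it looks. Taper capsules are study medication, so the daily prompts may well continue, and the eight-week wording may simply mean the study period. Serious-event reporting in D5 has no Day 57 cut-off. This stands in part. These provisions let a participant report, but none of them asks, and the reporting clock in D5 starts only once investigators know of the event.

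The consent form, information sheet and other handouts listed in Appendix B are not reproduced, nor is the earlier trial protocol from which the taper was taken. An instruction or contact described there cannot be excluded.

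A reader might infer more: that participants face a withdrawal hazard without supervision, or that taper events will be lost. The documents support neither. The D1 warning about hypotension and syncope concerns dose increases and interrupted therapy, and it does not clearly describe a planned step-down. Participants withdrawn for significant side effects do receive medical attention as needed, and D5 sends severe effects immediately to the principal investigator and study physicians.

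**Conclusion.** The point holds as a minor gap in safety ascertainment. Study drug is scheduled beyond the last adverse-event query, which leaves 3 to 5 dosing days per completer, or about 204 to 340 doxazosin dosing days among 68 expected completers. The range reflects the unstated time of the Day 57 dose and the disagreement between Table 2 and the C4 text on taper length. It rests on 85% completion in each arm and on the full taper being followed. Early-withdrawal tapers have the same gap, apart from medical attention as needed.

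In the documents available, events on the taper are captured only if volunteered. That conclusion is limited by the consent form and handouts that could not be checked. The documents give no event rate for the taper, so no number of missed events is claimed. The efficacy outcomes are collected by Visit 3 and are unaffected. The case for acting is that the remedy is cheap, not that the expected harm is large.

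**What to change.** - Add one adverse-event check-in, on the existing phone or survey form, within a few days after the last taper dose. Time it from that dose and not from a fixed study day, so that it serves both completers and early withdrawals. The C5 rule of phoning participants who do not complete a survey can apply.
- Extend the reporting instruction in D2, item 5 and the daily prompts in C5 until that contact.
- Define participation as ending after the check-in. D2, item 6 and the Confidentiality section have linking identifiers destroyed when participation is completed, so contact details must be kept until then.
- Reconcile the four-day taper in Table 2 with the five days in the C4 text.

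**Cost.** One brief contact per participant. At an assumed 5 to 15 minutes each, 160 participants need 160 x 5/60 = 13.3 to 160 x 15/60 = 40 staff hours over the whole trial. Some non-response is likely, because C3 makes the final payment at the last study visit. No new visit, instrument or analysis is needed, but the end of participation has to be redefined in the text.
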